18.1.2. UNSOLICITED AEs, INCLUDING SAEs

For each study group, the incidence rates (frequencies and percentages) of participants/events with unsolicited AEs (any, related, grade 3, leading to medical advice and related grade 3 respectively), including serious AE, occurring within 43-days (Days 1-43) post-dose of study interventions at Day 1 will be presented by SOC and PT. The incidence rates of participants/events with any unsolicited AEs will be summarized by country.

18.1.2.1. Relationship to Study Vaccination

Causality, as indicated by the Investigator is classed as “related” and “not related” to VNS/VV or MMR or *Havrix* or *Prevnar 13*. A “related” AE is defined as an AE with a relationship to study intervention as “related”. If a participant reports the same AE more than once within that SOC/PT, the AE with the worst-case relationship to study intervention will be used in the corresponding relationship summaries for each vaccination group.

18.1.3. UNSOLICITED AEs, EXCLUDING SAEs

For each study group, the incidence rates (frequencies and percentages) of participants/events with unsolicited AEs, excluding serious AE, occurring within 43-days (Days 1-43) post-dose of

Document: \\quintiles.net\\enterprise\\Apps\\sasdata\\SASb\\SAS\\GlaxoSmithKline\\VNS\\217212\\VNS 20-006\\Biostatistics\\Documentation\\SAP\\GSK_217212\\VNS 20-006_ZZA47662_SAP_Final_v7_24Jun2024.docx

Author: PPD Version Number: 7.0
Version Date: 24Jun2024

Template No.: CS_TP_BS016 Revision 6

Reference: CS_WI_BS005

Effective Date: 02Dec2019

study interventions at Day 1 will be presented by SOC and PT.

Immediate unsolicited AE is defined as an unsolicited AE that occurred within 30 minutes of vaccination. The immediate unsolicited AE flag is derived as follows: If the AE does not occur on the day of vaccination the flag is set to 'N'. Otherwise, if the AE occurs on the day of vaccination but happened before the vaccination then the flag is also set to 'N'. Otherwise, if the AE occurs on the day of vaccination and AE DATETIME minus Vaccination DATETIME is <= 30 minutes then set the flag to 'Y'. Otherwise, if the AE occurs on the day of vaccination and did not happen before the vaccination but either the time of vaccination or time of the AE is missing, then flag is set to 'U'. If the time of the AE is set to "00:00", then it will be assumed to be unknown and will be handled as missing. Immediate unsolicited AEs will be flagged in the listings.

18.1.4. SERIOUS AEs

For each study group, the incidence rates (frequencies and percentages) of participants with SAE occurring post-dose of study interventions at Day 1 will be presented by SOC and PT. Similar tabulation will be done for SAE with causal relationship to vaccination as assessed by the investigator; for fatal SAE and for causally related fatal SAE. Serious AEs will be recorded on the "Expedited Adverse Events" page of the eCRF. The incidence rates of participants with serious AEs will be summarized by country.

Listings of AEs and SAEs leading to discontinuation of study will be provided.

19. DATA NOT SUMMARIZED OR PRESENTED

The other variables and/or domains not summarized or presented are:

- Physical examination

These domains and/or variables will not be summarized or presented, but will be available in the

Document: \\quintiles.net\enterprise\Apps\sasdata\SASb\SAS\GlaxoSmithKline\VNS\217212\VNS 20-006\Biostatistics\Documentation\SAP\ GSK_217212\VNS 20-006_ZZA47662_SAP_Final_v7_24Jun2024.docx

Author: PPD Version Number: 7.0
Version Date: 24Jun2024

Template No.: CS_TP_BS016 Revision 6

Reference: CS_WI_BS005

Effective Date: 02Dec2019

clinical study database, SDTM and/or ADaM datasets.

APPENDIX 1. PROGRAMMING CONVENTIONS FOR OUTPUTS

IQVIA OUTPUT CONVENTIONS

Outputs will be presented according to the following IQVIA Output Conventions

Document Headers

All TFL is to include the following header:

GSK Vaccines
Vaccine: VNS and VV
Study 217212 (VNS 20-006) - DELIVERY DESIGNATION

where delivery designation is the name of the current delivery, e.g., DRY-RUN, FINAL ANALYSIS REPORT, etc

DATES & TIMES

Depending on data available, dates and times will take the form yyyy-mm-dd Thh:mm:ss.

SPELLING FORMAT

English US

PRESENTATION OF INTERVENTION GROUPS

For outputs, intervention groups will be represented as follows and in the given order:

Intervention Group	For Tables and Graphs	For Listings
VNS_Low	VNS Low	VNS Low
VNS_Med	VNS Med	VNS Med

Document: \\quintiles.net\enterprise\Apps\sasdata\SASb\SAS\GlaxoSmithKline\VNS\217212(VNS 20-006)\Biostatistics\Documentation\SAP\ GSK_217212(VNS 20-006)_ZZA47662_SAP_Final_v7_24Jun2024.docx

Author: PPD Version Number: 7.0

Version Date: 24Jun2024

Template No.: CS_TP_BS016 Revision 6

Reference: CS_WI_BS005

Effective Date: 02Dec2019

Intervention Group	For Tables and Graphs	For Listings
VNS_High	VNS High	VNS High
VV_Lot1	VV	VV Lot1
VV_Lot2		VV Lot2

PRESENTATION OF VISITS

For outputs, visits will be represented as follows and in that order:

Short Name	Long Name
Visit 1	Visit 1 (Day 1)
Visit 2	Visit 2 (Day 15)
Visit 3	Visit 3 (Day 43)
Safety Follow-up	Safety Follow-up (Day 181)

LISTINGS

All listings will be ordered by the following (unless otherwise indicated in the template):

- Randomized intervention group (or intervention received if it's a safety output), first by active dose [by ascending dose group] and then control,
- Center-participant ID,
- Date (where applicable).

DECIMAL PLACES

Decimal places for categorical data

Document: \\quintiles.net\enterprise\Apps\sasdata\SASb\SAS\GlaxoSmithKline\VNS\217212\VNS 20-006\Biostatistics\Documentation\SAP\ GSK_217212\VNS 20-006_ZZA47662_SAP_Final_v7_24Jun2024.docx

Author: PPD Version Number: 7.0
 Version Date: 24Jun2024

Template No.: CS_TP_BS016 Revision 6 Reference: CS_WI_BS005

Effective Date: 02Dec2019

- For percentages one decimal will be displayed.
- Differences in percentages and their corresponding confidence limits will be displayed with one more decimal than the maximum number used to display the individual percentages, for example the difference between two percentages displayed with one decimal will be displayed with two decimals.

Decimal places for Demographic and baseline characteristics will be as follows:

- The mean, median, and standard deviation for continuous baseline characteristics (age) will be presented with one decimal.

Serological Summary Statistics:

- The number of decimals used when displaying geometric mean concentrations (GMC) and their confidence limits is shown in the following table:

GMC value	Number of decimals
<0.1	3
≥0.1 and <10	2
≥10 and <1000	1
≥1000	0

When multiple categories of GMC values are present in the same table, the number of decimals displayed should match that of the smallest category (i.e., the one with the higher number of decimals). For example, if GMC values of <0.1 appear in the same table as values of ≥0.1 and <10 3 decimals should be displayed for both.

GMC ratios and their confidence limits will be displayed with 2 decimals regardless of the actual values.

Document: \\quintiles.net\\enterprise\\Apps\\sasdata\\SASb\\SAS\\GlaxoSmithKline\\VNS\\217212\\VNS 20-006\\Biostatistics\\Documentation\\SAP\\GSK_217212\\VNS 20-006\\ZZA47662_SAP_Final_v7_24Jun2024.docx

Author: PPD Version Number: 7.0

Version Date: 24Jun2024

Template No.: CS_TP_BS016 Revision 6

Reference: CS_WI_BS005

Effective Date: 02Dec2019

APPENDIX 2. PARTIAL DATE CONVENTIONS

Imputed dates will NOT be presented in the listings.

When partially completed dates (i.e., with missing day or month) are used in calculations, the following standard rules will be applied:

- A missing day will be replaced by 15
- A missing day and month will be replaced by June 30th.

The following exceptions apply:

- Adverse event start dates with missing day:
 - If the event starts in the same month as the study intervention, the contents of AE.AESTRTPT (the flag indicating if the event occurred before or after vaccination) will be used to complete the date. If 'after vaccination' is selected, the imputed start date will match study dose given during that month. If 'before vaccination' is selected, the imputed date will be one day before the study intervention given during that month.
- Adverse event start dates with missing day and month:
 - If the event starts in the same year as study intervention, the contents of AE.AESTRTPT (the flag indicating if the event occurred before or after vaccination) will be used to complete the date. If 'after vaccination' is selected, the imputed start date will match the study intervention given during that year. If 'before vaccination' is selected, the imputed date will be one day before the) study intervention given during that year.

All other cases of incomplete AE or concomitant medication/vaccination start date will follow the standard rules above.

Document: \\quintiles.net\enterprise\Apps\sasdata\SASb\SAS\GlaxoSmithKline\VNS\217212\VNS 20-006\Biostatistics\Documentation\SAP\ GSK_217212\VNS 20-006_ZZA47662_SAP_Final_v7_24Jun2024.docx

Author: PPD Version Number: 7.0
Version Date: 24Jun2024

Template No.: CS_TP_BS016 Revision 6

Reference: CS_WI_BS005

Effective Date: 02Dec2019

ALGORITHM FOR PRIOR / CONCOMITANT MEDICATIONS:

START DATE	STOP DATE	ACTION
Known	Known	If start date < study med start date, assign as prior If start date >= study med start date and start date <= Day 43, assign as concomitant
	Partial	Impute stop date as latest possible date (i.e., last day of month if day unknown or 31st December if day and month are unknown), then: If start date < study med start date, assign as prior If start date >= study med start date and start date <= Day 43, assign as concomitant
	Missing	If stop date is missing could never be assumed a prior medication If start date <= end of intervention, assign as concomitant
Partial	Known	Impute start date as earliest possible date (i.e., first day of month if day unknown or 1st January if day and month are unknown), then: If start date < study med start date, assign as prior If start date >= study med start date and start date <= Day 43, assign as concomitant

Document: \\quintiles.net\enterprise\Apps\sasdata\SASb\SAS\GlaxoSmithKline\VNS\217212\VNS 20-006\Biostatistics\Documentation\SAP\ GSK_217212\VNS 20-006_ZZA47662_SAP_Final_v7_24Jun2024.docx

Author: PPD Version Number: 7.0
 Version Date: 24Jun2024

Template No.: CS_TP_BS016 Revision 6

Reference: CS_WI_BS005

Effective Date: 02Dec2019

START DATE	STOP DATE	ACTION
	Partial	
Impute start date as earliest possible date (i.e., first day of month if day unknown or 1st January if day and month are unknown) and impute stop date as latest possible date (i.e., last day of month if day unknown or 31st December if day and month are unknown), then:
 
If stop date < study med start date, assign as prior
 
If stop date >= study med start date and start date <= end of intervention, assign as concomitant

	Missing	
Impute start date as earliest possible date (i.e., first day of month if day unknown or 1st January if day and month are unknown), then:
 
If stop date is missing could never be assumed a prior medication
 
If start date <= end of intervention, assign as concomitant

Missing	Known	If stop date < study med start date, assign as prior
	Partial	
Impute stop date as latest possible date (i.e., last day of month if day unknown or 31st December if day and month are unknown), then:
 
If stop date < study med start date, assign as prior

	Missing	Assign as concomitant

Document: \\quintiles.net\enterprise\Apps\sasdata\SASb\SAS\GlaxoSmithKline\VNS\217212\VNS 20-006\Biostatistics\Documentation\SAP\ GSK_217212\VNS 20-006_ZZA47662_SAP_Final_v7_24Jun2024.docx

Author: PPD Version Number: 7.0
 Version Date: 24Jun2024

Template No.: CS_TP_BS016 Revision 6

Reference: CS_WI_BS005

Effective Date: 02Dec2019

Certificate Of CompletionEnvelope Id: **PPD**

Status: Completed

Subject: Complete with DocuSign: GSK_217212(VNS 20-006)_ZZA47662_SAP_Final_v7.0_24Jun2024.docx

Project Code (Enter 0 for non-billable projects): **ZZA47662**IQVIA ID (Login ID): **PPD**

Business Unit:

DSSR

Source Envelope:

Document Pages: 46

Signatures: 2

Envelope Originator:

Certificate Pages: 5

Initials: 0

PPD

AutoNav: Enabled

EnvelopeD Stamping: Disabled

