15. MEDICATIONS

The percentage of participants who started medications after study vaccination will be presented by intervention group for the ES. Medications will be presented by Anatomical Therapeutic Chemical (ATC) classification and preferred drug name and by intervention group.

See APPENDIX 2 for handling of partial dates for medications, in the case where it is not possible to define a medication as prior or concomitant, the medication will be classified by the worst case; i.e., concomitant.

- ‘Prior’ medications are medications which started prior to the dose of study vaccination at Day 1.
- ‘Concomitant’ medications are medications which started on or after the day of the administration of study vaccination at Day 1.

Further details are in Section 6.8 of the Protocol. Concomitant medications which started from Day 1 to Visit 3 blood sample will be presented in table summaries (Any, antipyretic action) and in listings for all medications.

Document: \\quintiles.net\enterprise\Apps\sasdata\SASb\SAS\GlaxoSmithKline\VNS\217212(VNS 20-006)\Biostatistics\Documentation\SAP\ GSK_217212(VNS 20-006)_ZZA47662_SAP_Final_v7_24Jun2024.docx

Author: PPD Version Number: 7.0
Version Date: 24Jun2024

Template No.: CS_TP_BS016 Revision 6 Reference: CS_WI_BS005

Effective Date: 02Dec2019

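### SAP Appendix 2 labels some incompletely dated medications in the opposite direction to the worst-case rule in SAP Section 15

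*SAP*

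**What the plan says.** SAP Section 15 gives two definitions, both based on the start date. A start before the Day 1 dose makes a medication prior. The other class is defined by the statement that concomitant "medications are medications which started on or after the day of the administration of study vaccination at Day 1". It refers to Appendix 2 for partial dates and adds that, when neither label can be established, "the medication will be classified by the worst case; i.e., concomitant". The summary table (any medication; antipyretics) covers starts from Day 1 to the Visit 3 blood sample.

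SAP Appendix 2 contains two sets of rules. Its standard rules, which are said to cover incomplete concomitant medication start dates, include "A missing day will be replaced by 15", and use June 30th when the month is missing too. The algorithm table that follows says instead, for partial starts, "Impute start date as earliest possible date". Where the start is known and the stop is known or partial, the algorithm reads "If start date >= study med start date and start date <= Day 43, assign as concomitant". Where the stop is missing, the record can never be prior, and the rule is "If start date <= end of intervention, assign as concomitant".

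The SAP version history records that version 5 changed the algorithm to bring it into line with Section 15.

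**The concern.** Section 15 sends doubtful cases to concomitant, so that medication use after vaccination is not missed. An algorithm that sends doubtful cases to prior does the reverse and undercounts that use. Antipyretic use is part of the context for reading fever, which is a solicited endpoint over Day 1 to Day 43. There is also a programming problem: with two imputation rules and no stated precedence, two programmers could derive different labels from the same record.

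**Working it through.** **Inputs.** Definitions and fallback: SAP Section 15. Row rules: SAP Appendix 2. Single dose: Protocol Section 7.1. Visit 3 window, Day 1 plus 35 to 56 days: SAP Section 7.4. The plan states no figure to reproduce.

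**Assumptions.** Vaccination is equally likely on each day of a 365-day year. True starts are spread evenly over Study Days 1 to 43. A partial date lacks only the day. Each course ends three days after it starts.

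**Partial start, known stop.** In a month of m days there are m(m+1)/2 pairs of dose day and same-month start day with the start on or after the dose. The imputed first of the month precedes the dose in all of them except the m pairs where the dose is on the 1st. The share labelled prior is therefore 1 − 2/(m+1).

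- m = 31: 93.75%. m = 30: 93.5%. m = 28: 93.1%.
- Whole year: pairs = 7×496 + 4×465 + 406 = 5,738. Doses on the 1st = 365. Prior = 5,738 − 365 = 5,373, and 5,373/5,738 = 93.6%.
- All true starts on Day 1 to 43: 365×43 = 15,695, and 5,373/15,695 = 34.2%. Starts in a later month are imputed after the dose and are labelled correctly.

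**Competing day-15 rule, same records.** The 15th precedes the dose when the dose day is 16 or later. With k = m − 15 there are k(k+1)/2 such pairs: 136, 120 and 91 for 31, 30 and 28 days. The sum is 7×136 + 4×120 + 91 = 1,523, and 1,523/5,738 = 26.5%. One appendix therefore gives 93.6% or 26.5% prior, where Section 15's worst case gives 0%.

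**All rows, true start on Day 1 to 43.** *End of intervention* is undefined, so it was tried as Day 1, Day 43 and Day 181.

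| Start / stop | Result under Appendix 2 |
|---|---|
| Known / known or partial | 100% concomitant; agrees with Section 15 |
| Known / missing | No category: 42/43 = 97.7% if Day 1; 0% if Day 43 or Day 181 |
| Partial / known | 34.2% prior |
| Partial / partial or missing | 0% prior; no category: (15,695 − 5,738)/15,695 = 63.4% if Day 1; 0% if Day 43 or Day 181 |
| Missing / known or partial | 100% reach no branch, because only a stop before the dose has an action |
| Missing / missing | 100% concomitant; agrees with Section 15 |

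**Known start before the dose, missing stop.** Section 15 says prior. Appendix 2 gives concomitant in 100% of these under all three readings.

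**Upper limit.** A Visit 3 sample taken 56 days after Day 1 is on Study Day 56 + 1 = 57. A fully dated start on Study Days 44 to 57 gets no category in the algorithm, although it can precede an in-window sample.

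**The case against.** The case for leaving the text alone has real force. Protocol Section 6.8 requires start and end dates, and the schedule asks about medication at Day 1, Day 2-3, Day 15 and Day 43, so incomplete dates may be few. Section 15's fallback can be read as catching every record that Appendix 2 leaves unlabelled. A known start after the dose is concomitant by Section 15's definition whatever the stop row says. A known pre-dose start mislabelled concomitant is removed by the table's own start-date criterion, and that error runs against an undercount. The SAP names the visit Visit 3 (Day 43), so the Day 43 limit may mean the visit, and the protocol collects AE-associated medication only for Day 1 to Day 43.

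Most of this stands, and it rules out some stronger readings. A reader might infer that the medication table is simply wrong. That does not follow, because starts on Day 1 to 43 with complete dates are classified as in Section 15. A reader might apply the 93.6% to every partial start. It belongs only to the row with a known stop; in the same scenario the other two partial-start rows give concomitant. A reader might also conclude that all ongoing medications started on Day 2 to 43 drop out. That requires *end of intervention* to mean Day 1, which the documents do not say.

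The objection does not reach the partial-start, known-stop row. That row assigns a category, so the fallback for undecidable cases is never triggered. Nor does it settle which imputation rule takes precedence.

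**Conclusion.** The contradiction is established from the SAP's own text, and the version history indicates that it was not intended. The firm defects are:

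- the partial-start, known-stop row, which resolves doubt towards prior;
- two imputation rules for medication starts without precedence;
- a known pre-dose start that cannot be prior when the stop is missing.

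The undefined *end of intervention*, the absent branches for missing starts and the Day 43 limit are gaps whose effect depends on how they are read.

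The 93.6% and 34.2% are shares of affected records under the even-spread assumptions above, not shares of all medications. The documents do not say how many records have incomplete dates, so the overall effect is unknown. It is confined to incomplete dates and to starts between Day 44 and a late Visit 3. Only the descriptive medication tables (any, antipyretic) are touched. The GMC and seroresponse analyses and the fever percentages do not use this label.

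**What to change.** Replace the Appendix 2 table with one rule that follows Section 15.

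- A known start decides: before the dose is prior, whatever the stop date; on or after the dose is concomitant.
- If a partial or missing start could be on or after the dose, and the stop is not known to be before it, assign concomitant. Otherwise assign prior.
- Delete *end of intervention*, and delete the day-15/June 30th rule for medication starts.
- Put no upper limit on the classification. A limit there would leave later starts, and participants without a sample, uncategorised. Apply the Visit 3 blood sample date (or Day 43 if no sample was taken) only as the filter for the summary table.

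Under this rule no medication started on or after the dose is labelled prior when its dates leave the order open, and no record lacks a category. The price is that some incompletely dated medications truly started before the dose will count as concomitant, which is the direction that Section 15 already chose. The cost is SAP wording and one derivation; no new data are needed.
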